CLINICAL STUDY PROTOCOL SYNOPSIS

A phase I open-label multicentre dose-escalation study of subcutaneous ALM201 in patients with advanced ovarian cancer and other solid tumours

Study Protocol: ALM201/0001

Study Drug(s): ALM201

Version No: F2.0

Version Date: 24 SEP 14

EudraCT No: 2014-001175-31

NCT No: 03427073

Sponsor: Almac Discovery
[name]
[name]
[name]
[name]
UK

[contact]
[contact]

PROTOCOL SYNOPSIS

Protocol No:

ALM201/0001

Study Title:

A phase I open-label multicentre dose-escalation study of subcutaneous ALM201 in patients with advanced ovarian cancer and other solid tumours.

Investigational Product:

ALM201

Phase of Development:

1

No of Sites:

For dose escalation (Part 1): 3 UK sites

For further assessment of the Maximum Tolerated Dose (MTD), Maximum Feasible Dose (MFD) and/or Biologically Active Dose (BAD) in Part 2: up to 5 additional UK sites may be added in order to ensure there is an acceptable enrolment rate.

No of Patients:

The final sample size will depend on the number of Dose Limiting Toxicities (DLTs) observed at each dose level and any Cohort Review Committee (CRC) decision to assess an alternative treatment schedule in Part 1, plus the number of enrichment cohorts assessed at the MTD, MFD and/or BAD in Part 2.

Up to 36 evaluable patients would be anticipated for Part 1 based on a conservative estimate of enrolling a maximum of 36 patients across 6 dose escalation cohorts. Up to an additional 12 patients may also be enrolled to Part 1 for the assessment of alternative dose schedule(s).

No more than 36 evaluable patients will be enrolled for Part 2. This upper limit is based on an estimate of up to 12 patients being evaluated at 3 dose levels of interest.

Study Objectives and Endpoints:

The primary objectives of this study are to characterize the safety and tolerability of ALM201 and to identify a recommended phase 2 dose and schedule of administration of ALM201 in patients with advanced ovarian cancer.

Objective	Endpoint(s) (Assessment)
Primary:	

 To characterise the safety and tolerability of ALM201 (Parts 1 and 2) To identify a recommended phase 2 dose and schedule of ALM201 (Part 2 only) 	
 Ongoing evaluation of AEs during treatment and follow up; evaluation of DLT during Cycle 1 (Part 1 only) Safety, PK, PD and tumour response assessments
Secondary:	

 To establish the pharmacokinetic profile of ALM201 To assess anti-tumour activity To assess anti-tumour activity in a biomarker-enriched group of patients with advanced ovarian cancer (Part 2 only) 	
 Assessment of pharmacokinetic variables (including C_{max}, C_{min}, AUC) Tumour response assessment by RECIST 1.1(Eisenhauer et al, 2009ⁱ) and/or other relevant response assessments for tumour types enrolled Tumour response assessment by RECIST 1.1(Eisenhauer et al, 2009ⁱ)
Exploratory:	

 To assess relevant tumour biomarkers and the pharmacodynamic activity of ALM201 	
 Assessment of relevant tumour biomarkers and markers of ALM201 activity 
 in archival and/or fresh tumour biopsy material e.g. CD44, FKBPL, CD31, pFAK, pHer2, ITGA5, CA-125, ER, PR, angiogenesis signature and other relevant or exploratory biomarkers as appropriate for tumour type in blood e.g. RASSF1 methylation, and other relevant or exploratory biomarkers appropriate for tumour type in ascites (Part 2 only) e.g. stem cell count, and other relevant or exploratory biomarkers appropriate for ovarian cancer

Study Design:

This is a Phase 1, open-label, dose escalation study of the safety, tolerability, and pharmacokinetics (PK) of ALM201. The study will commence by enrolling patients with advanced solid tumours in whom treatment with an anti-angiogenic agent is appropriate. Eligible participants will be enrolled in sequential cohorts treated with ALM201, given as a sub-cutaneous (SC) injection while being monitored for safety and DLTs.

Dose levels will not be weight-adjusted and the starting dose for the study will be 10 mg ALM201 given on Days 1-5, 8-12 and 15-19 every 21 days i.e. weekday dosing. Dose increments will not exceed 100% and will be guided by safety data observed during Cycle 1, as well as on-going assessment of safety beyond Cycle 1 in earlier cohorts, plus PK and PD data as available. Every new dose cohort will be evaluated for the occurrence of a DLT during Cycle 1 of treatment ([Section 4.2.1](#)).

Accelerated enrolment followed by a 3+3 design

Part 1 of the study will commence with an accelerated dose escalation schedule and enrol 1 patient into a cohort with follow up for adverse events (AEs) and DLT during Cycle 1. The CRC will meet as soon as possible once the final study visit in Cycle 1 has taken place in each cohort to review patient safety data to the end of Cycle 1. Where there are no safety concerns, a 100% dose escalation step will be permitted for the next cohort. Where the CRC suspects that drug-related events have occurred that could progress to DLT upon further dose escalation e.g. clinically significant NCI (National Cancer Institute) CTCAE (Common Terminology Criteria for Adverse Events) Grade 2 events considered to be related to ALM201, they will confirm that future cohorts must enrol at least 3 patients in order to more thoroughly evaluate potential drug-related adverse events. The CRC may also advise that the current dose level under evaluation be expanded to 3 patients prior to further dose escalation in order to help inform the next dose escalation step. Dose escalation of 3-patient cohorts will proceed according to the scheme presented in [Section 4.2](#). Note that there will always be stagger of at least 1 week between dosing the first and subsequent patients in a new dose cohort. The CRC may request there be a further or prolonged stagger introduced during the trial, depending on the nature of adverse events observed to date.

Dose Limiting Toxicity

The CRC will agree on the next appropriate dose escalation step for each cohort primarily based on DLT evaluation during Cycle 1 of the current cohort. Only events occurring during the first cycle of treatment will be considered for DLT determination; however, there will be on-going evaluation of AEs in subsequent treatment cycles during the cohort review process. Clinically significant events thought to be potentially related to ALM201, or trends in adverse events seen in subsequent cycles will be taken into account when considering future dose escalation steps and dose administration schedules.

Upon occurrence of the first DLT in any cohort, additional patients will be added to that cohort so that up to a total of 6 can be evaluated. Once expansion to a 6-patient cohort has been recommended due to the identification of a DLT, escalation to the next 3-patient cohort will only occur when all patients in the expanded cohort have completed their first cycle of ALM201 and no more than 1 DLT has occurred. If 2 or more DLTs occur in an expanded cohort, DLT is established and the next lower dose level will be declared the MTD.

The highest dose where ≤ 1 DLT is seen in 3 or 6 patients will be termed the MTD. Note that intermediate dose levels may be explored below the dose level where ≥ 2 DLTs were seen, in order to identify the maximum dose which may be adequately tolerated. The CRC may also specify a recruitment stagger to be followed during cohort expansion for DLT evaluation depending on the nature of the DLT and the considered risk to patients.

In the case where an MTD is not established, the maximum feasible single dose which may be administered will be dictated by the formulation of ALM201 and the maximum volume for SC administration i.e. 3 x 1 mL injections, which will administer a dose of 300 mg ALM201 ([Section 6](#)). Should this dose be reached without the need to de-escalate due to DLT, it will be termed the MFD.

Based on the review of PD data in conjunction with on-going safety and PK data, the CRC may also identify a BAD for further exploration in Part 2 of the study.

Safety evaluations will be conducted weekly during each treatment cycle, with DLT assessed during Cycle 1 only. All events and suspected DLTs will be graded according to the CTCAE v4.03.

A DLT is defined as a Grade 3 or 4 AE that, in the opinion of the CRC, is likely to be related to ALM201 and represents a clinically significant hazard to the subject. Qualifying DLT events must be considered to be clinically relevant e.g. in duration, apparent reversibility, required management, and upon consideration of the patient's medical history and/or concomitant medications. DLT events must also be evaluated in terms of what is considered to be an appropriate next escalation step: in the case where the CRC agree that an escalation step of approximately 33% or lower is merited, the toxicity of concern should be declared a DLT.

Examples of exceptions that will be considered by the CRC are as follows:

- Grade 3 or 4 laboratory abnormalities, which resolve spontaneously or can be corrected with appropriate treatment (such as electrolytes) e.g. an event returns to baseline or to Grade 1 or less prior to the next administration);
- Symptomatic adverse events, such as nausea, vomiting and diarrhea, if they can be reduced to less than Grade 3 with standard supportive measures, such as anti-emetics and anti-diarrhoeals within 72 hours.

In order to be evaluable for DLT assessment, a patient must have received at least 80% of their scheduled doses (e.g. 12 of the 15), unless this lack of compliance is due to ALM201-related toxicity. DLT events must therefore be considered in terms of inability to administer the planned Cycle 1 dose administration schedule, and in such cases a dose delay of more than 14 days due to a toxicity event considered related to ALM201 will be considered to be a DLT ([Section 4.4.1](#)).

Part 1: Dose Escalation

In the absence of DLT or suggestion of ALM201-related adverse events which would lead to more cautious dose escalation, the following table presents a hypothesised dose escalation plan:

Cohort	Escalation Step	Dose level
1 (Starting Dose)	-	10 mg
2	(2X starting dose)	20 mg
3	(4X starting dose)	40 mg
4	(8X starting dose)	80 mg
5	(16X starting dose)	160 mg
6 (MFD)	(30X starting dose)	300 mg

The dose may be doubled in sequential cohorts where the CRC consider it appropriate to do so, based on on-going evaluation of DLTs and adverse event data. Dose escalation decisions will also take available PK and pharmacodynamic (PD) data into consideration.

In the case where a potentially significant toxicity occurs, or a trend in toxicities is seen, considered to be related to treatment with ALM201 and potentially a precursor to a clinically significant toxicity event, subsequent dose escalation steps will be more conservative and will not exceed 50% of the previous dose. This restriction may be reversed where there is no suggestion of potentially clinical significant toxicity in subsequent cohort(s). In the case where a single DLT event is confirmed in an expanded cohort, the next dose escalation step will not exceed 33% of the previous dose. However, where there are no further events seen in the next cohort; the CRC may allow future dose escalation steps of up to 50%.

Note that the CRC may also recommend that an MTD, MFD or BAD be assessed in a cohort of 6 patients in Part 1 where only 3 patients have received this dose level to date, prior to recommending the enrolment of an enrichment cohort to receive this dose level in Part 2.

Cohort Review Committee

All dose escalation decisions will be made by a CRC who shall convene to review all available AE, PK, PD and relevant patient data ([Section 8.1](#)). Patients in Part 1 will be eligible for DLT evaluation if they have received 80% e.g. 12 of their 15 scheduled doses, during Cycle 1. The CRC will be composed of the trial investigators, a patient representative, sponsor representative(s) and the study Medical Monitor. Additional experts may be invited to support the review of the data as required e.g. a pharmacokineticist. The Contract Research Organisation (CRO) responsible for managing and monitoring the trial will also support the preparation and conduct of the CRC meetings and may attend such meetings. All data reviewed, CRC discussions and agreed dose escalation recommendations will be minuted. The composition of the CRC and the data review processes to be followed by the committee will be fully described in a CRC Charter.

Based on on-going safety, PK and PD data evaluation, the CRC may also recommend dose de-escalation steps or adjustments in the dose administration schedule of ALM201. Upon review of available safety, PK and PD data, the CRC may recommend that an alternative dose administration schedule of ALM201 be explored. Less intense dose administration schedules will be permitted as long as the unit dose does not exceed the next permitted escalation step. Given the starting dose administration schedule is week-day dosing i.e. D1-5, D8-12, D15-19, on a 21 day cycle, a more dose intense dosing schedule is unlikely. However, should the CRC consider this reasonable to explore, the same dose escalation rules will apply and pharmacokinetic modelling, in conjunction with the safety data obtained to date, will be used to inform the appropriate dose level for a more dose intense dose schedule.

Note that the MTD or MFD need not be confirmed for the original dose administration schedule prior to the CRC recommending the investigation of an alternative dose administration schedule. Multiple dose escalation tracks may be followed if more than one dose schedule is considered relevant to explore i.e. the CRC may recommend that the alternative dose administration schedule

replaces a schedule or is explored in addition to another schedule, as long as dose escalation rules are not exceeded.

Duration of treatment

The main study will permit a maximum of 8 three-weekly treatment cycles (or approximately 6 months of treatment). Patients who are seen to potentially be benefiting from treatment i.e. patients whose disease has not progressed and who have not been withdrawn from therapy due to toxicity, will be eligible to continue to receive additional cycles of ALM201 where this is recommended by their study physician, subject to availability of ALM201. Such patients will continue to be followed up for compliance, toxicity and continued response ([Schedule of Study Assessments](#)).

Part 2: Enrichment at MTD, MFD and/or BAD

Once an MTD, MFD and/or BAD has been established for a given dose and schedule in Part 1, Part 2 may commence. Part 2 will involve up to an additional 36 patients with advanced ovarian cancer. During Part 2 of the study there will be on-going evaluation of safety and the opportunity to obtain preliminary anti-tumour activity at each dose level selected in the ovarian cancer population. The only dose adjustments permitted in Part 2 will be dose de-escalations (based on a de-escalation of the unit dose or a less frequent administration schedule of the maximum unit dose). Such decisions will be driven by each patient's tolerability of ALM201. Where possible, such dose reductions should be made by the CRC who can convene on an ad-hoc basis to advise on the appropriate dose adjustment; however, the investigator may implement a dose reduction prior to CRC review in the interest of patient safety.

Study Assessments:

The study will commence with a dosing schedule of ALM201 monotherapy given SC on Days 1-5, 8-12 and 15-19 in a 3 week cycle.

Patients will have scheduled site visits on every dosing day of the first cycle, then on Days 1, 8 and 15 of Cycles 2-4. From Cycle 5 onwards, they are only required to visit the clinic on Day 1 of each cycle. ALM201 administration can be given at home on all other days.

Safety assessments will include physical examination, vital signs, biochemistry and haematology laboratory screens, plus immunogenicity testing (see [Schedule of Study Assessments](#)). Adverse events will also be noted at every clinical visit and recorded at least every week. For all administrations in hospital, the patients must wait for at least 60 minutes from the time of the ALM201 injection for observation and repeat vital signs. These precautions are in case of emergent evidence of immunogenicity in Cycle 1, and at other times after the weekend break in dosing.

Tumour assessment by imaging (computed tomography (CT) scan or magnetic resonance imaging (MRI) scan as appropriate for tumour type) will be assessed in all patients at Screening and after every 2 cycles of treatment (i.e. every 6 weeks) during Cycles 1-8 (first 24 weeks), and then after every 4 cycles of treatment (i.e. every 12 weeks) from Cycle 9 onwards. Scans may be performed at other times as clinically indicated.

Tumour assessment by informative tumour markers where relevant for tumour type e.g. GCIG

criteria for CA125 (Rustin, et al. 2011ⁱⁱ), PSA, CEA or CA19-9, will be assessed in all patients at Screening and after every 2 cycles of treatment during treatment (i.e. every 6 weeks). Tumour markers may be performed at other times as clinically indicated.

A PK profile for ALM201 will be taken on Days 1, 3 and 18 of Cycle 1 and on Day 18 of Cycles 2, 4, 6 and 8. Pre-dose samples will also be taken on Cycles 2-8 on Day 1.

All patients will be asked to provide consent for access to archived tumour tissue where available, and where possible, fresh biopsies will be taken pre-dose and again during the study where the patient has a documented tumour response and/or at the point of disease progression to allow for potential biomarker and pharmacodynamic assessment. In Part 2, access to a tumour biopsy sample will be required to confirm each patient's eligibility for the study (see Inclusion Criterion 2). A fresh biopsy will be preferable for this purpose; however, where it is not possible to obtain this, confirmation of the angiogenesis signature may be performed on archived tumour tissue during Screening. In Part 2, there will also be additional biomarker/PD assessments in blood and ascites. In both parts of the study, any remaining samples obtained for biomarker/PD assessment will be retained for potential future analysis.

Patients will be withdrawn from the study at the point of receiving their last dose of ALM201. However, all patients will be asked to participate in a protocolled follow up assessment 4 weeks after their last dose for safety assessments. Furthermore, patients will continue to be followed up either in the study clinic or by telephone contact every 8 weeks ([Schedule of Study Assessments](#)) for up to approximately a 2 year period, to check their disease (survival) status and commencement of next anti-cancer treatment.

Inclusion/Exclusion Criteria:

Part 1 will enrol patients with advanced solid tumours in whom treatment with an anti-angiogenic agent is appropriate. Part 2 will enrol patients with ovarian cancer, screened using an angiogenesis gene signature, that have failed to respond to, or have relapsed following standard therapy.

Inclusion Criteria

(i) Part 1 Specific Inclusion Criterion

1. Patients with histologically and/or cytologically confirmed advanced solid tumour for whom no standard effective therapy is available or felt likely to be of limited efficacy and in whom a rationale for use of an anti-angiogenic treatment approach exists. Note: *Previous use of anti-angiogenic therapy is allowed if tolerated*

(ii) Part 2 Specific Inclusion Criterion

2. Patients with advanced ovarian cancer, who are intolerant of or whose tumour is resistant to platinum and who have failed to respond to, or have relapsed following, standard therapy and whose tumour has a proangiogenic profile as assessed by the angiogenesis gene signature test. Note: *Previous use of anti-angiogenic therapy is allowed if tolerated.*

(iii) General Inclusion Criteria for all Patients

3. Adult patients defined by age ≥ 16 years at time of consent.
4. Evaluable disease, either measurable on imaging, or with informative tumour marker(s), as assessed by RECIST 1.1 (Eisenhauer et al, 2009¹) or other relevant response assessment criteria for tumour type.
5. Recovery from previous treatment to baseline or CTCAE \leq Grade 1, as determined by CTCAE v4.03 criteria ([Appendix B](#)), of reversible toxicities related to prior treatment, with the exception of alopecia, lymphopenia, other non-clinically significant adverse events; recovery from previous radiotherapy other than residual cutaneous effects or stable $<$ Grade 2 gastrointestinal toxicity; complete recovery from surgery other than stable $<$ Grade 2 toxicity.
6. Eastern Collaborative Oncology Group (ECOG) Performance Status (PS) of 0 or 1 ([Appendix A](#)).
7. Laboratory values at Screening:
 - Absolute neutrophil count $\geq 1.5 \times 10^9/L$ without colony stimulating factor support;
 - Platelets $\geq 100 \times 10^9/L$;
 - Haemoglobin ≥ 9 g/dL (not transfusion dependent);
 - Total bilirubin < 1.5 times the upper limit of normal (ULN) (unless due to Gilbert's syndrome where it should be $\leq 2.5 \times$ ULN);
 - AST (SGOT) ≤ 2.5 times the ULN; ALT (SGPT) ≤ 2.5 times the ULN; $\leq 5 \times$ ULN for patients with advanced solid tumours with liver metastases; patients with confirmed bony metastases will be permitted on study with isolated elevations in ALP < 5 times the ULN;
 - Serum creatinine $\leq 1.5 \times$ ULN or estimated glomerular filtration rate (GFR) of > 50 mL/min based on the Cockcroft-Gault formula ([Appendix D](#));
 - Normal coagulation (elevated INR, prothrombin time or APTT $\leq 1.3 \times$ ULN range acceptable);
 - Urine protein $\leq 2+$ (as measured by dipstick).
8. Negative urine or blood human chorionic gonadotropin (hCG) test during Screening and within 7 days of Cycle 1, Day 1 in women of childbearing potential (defined as women ≤ 50 years of age or history of amenorrhea for ≤ 12 months prior to study entry). Sexually active male and female patients of childbearing potential must agree to use an effective method of birth control e.g. barrier methods with spermicides, oral or parenteral contraceptives and/or intrauterine devices, during the entire duration of the study and for 6 months after final administration of ALM201. Note that sterility in female patients must be confirmed in the patients' medical records and can be defined as any of the following: surgical hysterectomy with bilateral oophorectomy, natural menopause with menses > 1 year ago; radiation induced oophorectomy with last menses > 1 year ago; chemotherapy induced menopause with 1 year interval since last menses.

9. Ability to give written, informed consent prior to any study-specific Screening procedures, with the understanding that the consent may be withdrawn by the patient at any time without prejudice.
10. Patient is capable of understanding the protocol requirements, is willing and able to comply with the study protocol procedures, and has signed the informed consent document.

Exclusion Criteria for all Patients

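### The rule that closes a dose can name an MTD seen in only 1 patient, contrary to the 3-or-6-patient definition in the next paragraph, and nothing in the synopsis expressly requires that lower dose to be filled up first

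*Protocol*

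**What the plan says.** **How cohorts start.** Under the heading on accelerated enrolment followed by a 3+3 design, the protocol synopsis says that Part 1 will "commence with an accelerated dose escalation schedule and enrol 1 patient into a cohort", with doubling allowed while there are no safety concerns. If the Cohort Review Committee (CRC) suspects drug-related events that could progress to DLT, "they will confirm that future cohorts must enrol at least 3 patients". For the level then being studied, the wording is permissive: "The CRC may also advise that the current dose level under evaluation be expanded to 3 patients prior to further dose escalation".

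**How a dose closes.** Under Dose Limiting Toxicity: "Upon occurrence of the first DLT in any cohort, additional patients will be added to that cohort", up to 6 in total. Then: "If 2 or more DLTs occur in an expanded cohort, DLT is established and the next lower dose level will be declared the MTD".

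**How the MTD is defined.** The next paragraph says: "The highest dose where ≤ 1 DLT is seen in 3 or 6 patients will be termed the MTD". It adds that intermediate doses may be explored below a level with 2 or more DLTs.

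**Confirmation and use.** Under Part 1: Dose Escalation, the CRC may have an MTD "assessed in a cohort of 6 patients in Part 1 where only 3 patients have received this dose level to date". Under Part 2: "Once an MTD, MFD and/or BAD has been established for a given dose and schedule in Part 1, Part 2 may commence".

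**SAP.** Section 3.1 repeats the 3-or-6 definition and the option of intermediate doses, but not the closing sentence. Section 1 states that the sponsor halted the study at the end of Part 1.

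**The concern.** The closing sentence looks only at the dose that failed. It then labels the dose below without asking how many patients were treated there. That is harmless when the lower dose already has 3 or 6 patients with at most 1 DLT, because closing rule and definition then agree. It is not harmless after accelerated escalation, when the lower dose may have had 1 patient.

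The same gap can follow the move to 3-patient cohorts. That move binds later cohorts only, so if the first 3-patient cohort fails, the level beneath it may still hold 1 patient.

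At stake is which dose carries the MTD label, or whether any dose does. In the full design that label could open Part 2, with an estimate of up to 12 patients per dose level and DLT evaluated in Part 1 only. With Part 2 cancelled, the label matters for the final report and for any later study that starts from it.

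**Working it through.** **1. The plan's own figure.** No of Patients gives up to 36 evaluable patients over 6 escalation cohorts: 6 × 6 = 36. This reproduces and is not in dispute.

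**2. Tracing the rules.** Suppose 10, 20, 40 and 80 mg are each clean in 1 patient. At 160 mg the first patient has a DLT, the cohort expands to 6, and a second DLT occurs.

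| Rule | Result |
|---|---|
| Closing sentence | 80 mg is the MTD, on 0 DLTs in 1 patient |
| 3-or-6 definition | No dose qualifies: none below 160 mg has 3 patients, and 160 mg has 2 DLTs |
| Maximum feasible dose | Not available: 300 mg was not reached without a DLT-driven stop |

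**3. How much 1 patient shows.** The exact one-sided 95% upper limit for the DLT rate with 0 events in n patients is 1 − 0.05^(1/n). For 1 event in 6 it solves (1−p)^6 + 6p(1−p)^5 = 0.05.

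| Result | 0/1 | 0/3 | 0/6 | 1/6 |
|---|---|---|---|---|
| Upper limit | 95% | 63% | 39% | 58% |

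**4. How readily a toxic dose passes.** The plan gives no DLT rates, so these are assumed. A dose with true rate p is clean in 1 patient with probability 1−p. It passes the 3-or-6 rule (0/3, or 1/3 then 0/3) with probability (1−p)^3 + 3p(1−p)^5.

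| Assumed p | Clean in 1 | Passes 3-or-6 |
|---|---|---|
| 0.30 | 70% | 0.343 + 0.151 = 49% |
| 0.40 | 60% | 0.216 + 0.093 = 31% |
| 0.50 | 50% | 0.125 + 0.047 = 17% |

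**5. Two adjacent one-patient levels.** With rates L (lower) and U (upper), the chance that the lower is clean, the upper has a DLT in its first patient, and at least 1 more occurs in the 5 added is (1−L) × U × [1−(1−U)^5].

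- 0.15 and 0.30: 0.85 × 0.30 × 0.832 = 21%
- 0.20 and 0.40: 0.80 × 0.40 × 0.922 = 29%
- 0.25 and 0.50: 0.75 × 0.50 × 0.969 = 36%

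**6. Whole-trial simulation.** Assumptions:

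- Start at 10 mg, cap at 300 mg.
- Logistic DLT curve in log dose, with rate 0.33 at 50, 100 or 200 mg and slope 1.5 or 2.5.
- One-patient cohorts with doubling. A clean one-patient cohort triggers the switch to cohorts of 3 with probability 0, 30% or 60%, with 50% steps afterwards.
- The first DLT expands the cohort to 6. One DLT in 6 gives a 33% step; 2 or more close the dose.
- The CRC uses none of its optional expansions or intermediate doses.

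Results are among trials that close a dose. The gain is the fall in the share whose declared MTD has a true rate above 0.33.

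| Switch probability | MTD rests on 1 patient | Gain from requiring 3 or 6 | Mean extra patients |
|---|---|---|---|
| 0 | 77–89% | about 17–24 points (0.33-rate dose 50 or 100 mg); none at 200 mg | 2.6–3.9 |
| 30% | 17–46% | 0–8 points | 0.6–1.8 |
| 60% | 2–21% | under 2 points | 0.1–0.7 |

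Filling can cascade, because a filled level may itself fail. With no switching, 14–35% of closing trials fill two or more levels, with up to about 20 extra patients.

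**The case against.** The strongest reply is that the synopsis largely shows which rule is meant. The 3-or-6 sentence is its only definition of the MTD and directly follows the closing rule. The confirmation option speaks of a level where only 3 patients have been treated, which suggests that 3 was regarded as the floor. SAP 3.1 carries the definition alone. This stands. A reader might infer two rules of equal standing, or an intention to accept a one-patient MTD, and the documents support neither. What survives is narrower: the closing sentence is mandatory in wording and has no minimum, while expanding the current level, exploring intermediate doses and confirming in 6 are all permissive.

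The reply also notes that the protocol file is a synopsis. It refers to Section 4.2 for 3-patient escalation and to the CRC Charter for the review process, and either may settle the point. That stands too, and limits the finding to the synopsis as worded.

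Thirdly, SAP 4.1 already has tables show the analysis-set size and use patients per dose level as denominators, and SAP 4.7.1 tabulates DLTs. A dose given to 1 patient would therefore be visible. The number evaluable for DLT would not necessarily be: SAP 3.6.2 describes evaluability, but SAP 3.5 defines no such population and safety tables use all treated patients.

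Finally, the 77–89% could be read as the chance of a wrong MTD. It is only the share of closing trials whose MTD rests on 1 patient, if no clean cohort triggers a switch and the CRC uses none of its options.

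**Conclusion.** The closing sentence is wrong as written, because followed literally it can name an MTD that the plan's own definition would not accept. The defect is one of wording against a definition that appears to be the intended rule, and it is confined to the case where the level just below the closed dose has fewer than 3 patients.

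Its size depends on assumptions that the plan does not supply: the DLT curve, and how early cohorts of 3 begin. The gain in avoiding an MTD with a true rate above 0.33 is material only if one-patient cohorts continue to the first DLT and that rate is reached around 50 or 100 mg. It is small otherwise.

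The documents do not report which doses were given, how many patients each had, or whether any dose was closed. A reader might infer that Part 1 produced a one-patient MTD; nothing here shows that. A reader might also infer that 2 DLTs in the first 3 patients would not close a dose, since the sentence mentions only expanded cohorts. The definition and the intermediate-dose provision imply that it would.

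**What to change.** Reword the closing sentence of the synopsis along these lines:

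> *When 2 or more DLTs have been seen at a dose level, no further patients start at that dose. The next lower level, or an intermediate one, becomes the MTD only after 0 DLTs in at least 3 evaluable patients or at most 1 in 6. A level with fewer than 3 patients is filled up first. If it fails, the same rule applies to the level below.*

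Add a line to SAP 3.1 with the same minimum, and report the number of DLT-evaluable patients behind any MTD. If Section 4.2 already says this, only the synopsis needs the wording. For a study that has finished escalating, the reporting line is the part that still has effect.

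The cost in patients is 2 per level filled, or 5 if a DLT takes that level to 6, sometimes over more than one level. The mean is about 2.6–3.9 per trial that closes a dose with no switching, under 2 at 30% switching and under 1 at 60%, on the assumptions above. On the six-level ladder, the longest accelerated path uses 5 × 1 + 6 = 11 patients. Filling one level makes this 13 or 16, and filling all five lower levels to 6 makes it 11 + 5 × 5 = 36. The change is therefore expected to fit the stated 36, although intermediate doses or smaller steps would lengthen the ladder. Where the lower level already has 3 or 6 patients with at most 1 DLT, nothing changes.
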